1. Pre- and postoperative cognitive dysfunction (assessed in ENT clinic at pre- and post-operative visits or at anesthesia preoperative clinic) with the Mini-Cog, Mini-Mental Status Examination (MMSE) and the Cognitive Failure Questionnaire (CFQ).
2. Pain assessment (Prior to surgery (baseline assessment upon study enrollment in ENT clinic) and postoperative days 0-3 (afternoon/evening on postoperative day 0, and POD 1-3 per Emory protocol every 4 hours). Assessed by observer-based Behavioral Pain Scale or Behavioral Pain Scale (Non-Intubated) with subsequent administration of patient-reported Visual Analog Scale.

October 8, 2019

3. Post-operative use of narcotics (assessed POD 0-3 from medical chart)
4. Off line EEG analysis to correlate with postoperative delirium

7. Participant Selection

Inclusion criteria:

Inclusion criteria:

1. Patients 18 years of age and older, with otolaryngeal cancer receiving surgery with general anesthesia.

(Please note we are purposefully including patients with higher predisposition to delirium as we are investigating potential preventive strategies for this diagnosis of multiple etiologies. Patients at higher risk of delirium (e.g., advanced age, chronic hypertension) will be included in our study. Additionally, other common risk factors that exist in this patient population (e.g., alcohol or nicotine use) are thought to contribute to delirium postoperatively. [19])

2. Competent to provide informed consent.

Exclusion criteria:

1. Emergency surgery
2. Monitored Anesthesia Care (i.e., regional anesthesia alone without plans for general anesthesia)
3. Surgery involving the eye, eyebrow, forehead, or frontal scalp near the sensor placement
4. Poor health literacy (see next section)
5. Patients with an allergy, or have experienced any drug reaction to ketamine will be excluded.
6. Pregnant or lactating patients
7. Patients in active alcohol withdrawal
8. Patients with chronic pain who are taking buprenorphine

Subject Replacement

Subjects who are not admitted to the Intensive Care Unit after surgery, will be replaced, but will be followed per protocol through the final visit 2-6 weeks post-operatively.

Recruitment Plan/Eligibility Screening:

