Patients undergoing surgical procedures requiring general anesthesia will first be approached for participation during the patient's preoperative visit, at the preoperative ENT clinic visit or on the day of surgery. A clinical research coordinator or other research personnel will be available to answer questions and obtain informed consent from the patient. It will be made clear to the patient that study participation is optional and that they can "opt out" at any time even if they have signed a consent form. In order to assure that our study participants are capable of understanding the information provided in the informed consent a single question screen will be used to detect inadequate health literacy: "How confident are you filling out medical forms by yourself?". This has been used in previous hospitals to detect poor health literacy [20]).

We intend on enrolling up to 100 male and female patients that meet eligibility criteria in order to have 60 patients who complete all study assessments. In addition to examining the potential effects of age, anesthetic drugs, and other patient and clinical factors on cognitive trajectories post-anesthesia, gender will be recorded and statistically examined as a potential contributor to different EEG patterns among our patients in this observational study.

8. Procedures:

- Upon enrollment, demographic data and medical history will be collected, subjects will be questioned about obstructive sleep apnea (OSA) using the STOP-Bang Questionnaire [21]). They will also be screened for cognitive impairment using Mini-Cog, Mini-Mental Status Examination (MMSE) and the Cognitive Failure Questionnaire (CFQ). A baseline pain assessment will be performed using the Visual Analog Scale. A baseline assessment of delirium will be obtained using the Confusion Assessment Method for Intensive Care Unit (CAM-ICU) criteria.
- Patients will be randomized to one of three groups on the morning of surgery by the Investigational Drug Service, before they enter the operating room. A randomization table will be provided and the subject assignment will be the next available number on the list. The study staff will be blinded to the list and the assignment. Group 1 will be given 0.5mg/kg of ketamine pre-incision as an intravenous (IV) bolus. Group 2 will receive 1.0mg/kg of ketamine pre-incision as

an IV bolus. Group 3. Will be administered saline/ placebo pre-incision an IV bolus. The provider will be blinded to the treatment assignment.

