- Upon arrival in the operating room, before the induction of anesthesia, disposable EEG sensors (SEDLine) will be applied over the forehead according to the manufacturer's instructions.
- The pads will be placed out of the surgical field. For surgical cases where patient positioning or surgical skin preparation may interfere with good sensor contact, tape or Tegaderm® patches will be applied over the sensors to ensure they stay dry and in place.
- The patient will then be induced according to standard of care at the anesthesiologist's discretion. After induction a single bolus dose of ketamine (0.5mg/kg or 1mg/kg) or saline placebo will be given intravenously.
- The operation itself will proceed in the usual fashion using the standard monitors placed in all such cases according to institutional practice. Operative characteristics will be recorded.
- At the conclusion of the operation, the anesthesia practitioner will press the event marker button to aid in synchronizing the EEG raw data. The provider will adhere to specific guidelines (Provider Instructions), data will be recorded and the EEG file (without patient identifiers) will be downloaded and stored securely.
- The sensor will be removed and EEG data will cease to be collected before transport to the recovery room.
- While in the recovery room, the patient's pain level will be assessed (observer-based Behavioral Pain Scale or Behavioral Pain Scale (Non-Intubated) with subsequent administration of patient-reported Visual Analog Scale) as standard of care. The patient will be screened for post-operative delirium using the CAM-ICU delirium score and the Richmond Agitation and Sedation Score (CAM-ICU; RASS) 30 minutes after arrival and at discharge.
- While in the ICU pain assessment will be performed on postoperative days 0-3 (afternoon/evening on postoperative day 0, and POD 1-3 per Emory protocol, that is typically recorded by staff every 4 hours). Assessed by observer-based Behavioral Pain Scale or Behavioral Pain Scale (Non-Intubated) with subsequent administration of patient-reported Visual Analog Scale. Available data will be

gathered from the medical chart including vasopressor use, ICU and hospital length of stay.

- The patient will be screened for post-operative delirium using the CAM-ICU delirium score and the RASS during the ICU stay, typically recorded three times a day per Emory SOC. Available data will be gathered from the medical record for POD 1-3.

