APPENDIX A- Study Flowchart and Schedule of Assessments

1 Just after anesthesia induction time

2 Assessment to occur in afternoon or evening, obtain VAS if possible

3 Pain assessments recorded for SOC, as available

4 CAM-ICU scores as recorded per SOC, during ICU stay, as available

5 Post op visit may occur at ~ 2 weeks and/or ~6 weeks

6 Adverse Events to be collected only after treatment with study product/placebo

7 30 minutes after PACU arrival and at PACU discharge

CAM-ICU Worksheet

Feature 1: Acute Onset or Fluctuating Course	Score	Check here if Present

Is the pt different than his/her baseline mental status? OR Has the patient had any fluctuation in mental status in the past 24 hours as evidenced by fluctuation on a sedation scale (i.e., RASS), GCS, or previous delirium assessment?
	Either question Yes →	
Feature 2: Inattention		

Letters Attention Test (See training manual for alternate Pictures)
 
Directions: Say to the patient, "I am going to read you a series of 10 letters. Whenever you hear the letter 'A,' indicate by squeezing my hand." Read letters from the following letter list in a normal tone 3 seconds apart.
 
S A V E A H A A R T
 
Errors are counted when patient fails to squeeze on the letter "A" and when the patient squeezes on any letter other than "A."
	Number of Errors >2 →	
Feature 3: Altered Level of Consciousness		
Present if the Actual RASS score is anything other than alert and calm (zero)	RASS anything other than zero →	
Feature 4: Disorganized Thinking		

Yes/No Questions (See training manual for alternate set of questions)
 
 1. Will a stone float on water? 2. Are there fish in the sea? 3. Does one pound weigh more than two pounds? 4. Can you use a hammer to pound a nail? 
Errors are counted when the patient incorrectly answers a question.
 
Command Say to patient: "Hold up this many fingers" (Hold 2 fingers in front of patient) "Now do the same thing with the other hand" (Do not repeat number of fingers) *If pt is unable to move both arms, for 2nd part of command ask patient to "Add one more finger"
 
An error is counted if patient is unable to complete the entire command.
	Combined number of errors >1 →	

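### Replacement is triggered by ICU non-admission after dosing, later CAM-ICU readings are sourced from the ICU stay, and section 10 names no analysis set, so a post-treatment-selected primary comparison is permitted

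*Combined protocol and SAP*

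**What the plan says.** **Order of events.** Section 8 has "Patients will be randomized to one of three groups on the morning of surgery", before they enter the operating room, with the bolus given after induction. The inclusion criteria in section 7 do not require planned ICU admission; any otolaryngeal cancer surgery under general anesthesia qualifies. Section 7, Subject Replacement, then says "Subjects who are not admitted to the Intensive Care Unit after surgery, will be replaced, but will be followed per protocol through the final visit", which is at 2 to 6 weeks.

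**Where delirium is read.** Section 6 defines the primary outcome as CAM-ICU delirium on POD 0-3. Section 8 adds recovery-room screens "30 minutes after arrival and at discharge", and Appendix A footnote 7 repeats this as "30 minutes after PACU arrival and at PACU discharge". After that, section 8 has screening "during the ICU stay, typically recorded three times a day per Emory SOC", and Appendix A footnote 4 gives the source for POD 0-3 as "CAM-ICU scores as recorded per SOC, during ICU stay, as available". The section 6 definition does not mention the recovery-room screens.

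**Who is counted.** Section 7 enrols up to 100 "in order to have 60 patients who complete all study assessments". Section 10a plans about 85 enrolled to reach 20 completed per arm. Section 10b calculates incidence by randomised group and compares each dose with placebo by Fisher's exact test. It names no analysis set, no treatment of replaced patients and no rule for missing readings.

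**Blinding.** Section 8 states "The study staff will be blinded to the list and the assignment"; the provider is blinded too.

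**The concern.** ICU admission is a post-treatment event here, yet it decides who is replaced and largely decides who has a primary outcome. A patient who bypasses the ICU has recovery-room screens and no specified source of POD 1-3 readings. A patient who leaves the ICU before POD 3 has a shortened observation window. A team that follows the plan literally is therefore drawn towards analysing ICU patients, a set that randomisation did not form.

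Two things are at stake. First, if ICU admission or ICU time differed between arms, by chance or through a drug effect, the arms compared would no longer be exchangeable. Second, with no stated set or reading rule, the choice could be made after outcomes are known. If loss is equal across arms, the cost is power only.

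**Working it through.** **1. The plan's own figure.** Inputs from section 10a: 30% on placebo (n=20), 5% on both ketamine arms combined (n=40), alpha 0.05, Mantel-Haenszel (MH) test read as one-sided. With a placebo events, m events in total and N=60, z = (a - 20m/60) / sqrt[20·40·m(60-m) / (60²·59)]; reject if z ≥ 1.645. Summing binomial probabilities over all tables gives **84.8%**, against the stated 85%. With 30% in every arm the rejection rate is 5.0%.

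**2. Is the outcome observed in everyone randomised?**

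| Patient | Recovery room | POD 0-3 after recovery room |
|---|---|---|
| In ICU through POD 3 | two screens | ICU charting, as available |
| Leaves ICU before POD 3 | two screens | ICU charting until discharge, then no specified source |
| Never in ICU (replaced) | two screens | no specified source |

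Only the first row has a specified source for the whole window.

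**3. Illustration: ICU-only analysis with unequal admission.** None of these inputs is in the documents: no drug effect; ICU placebo risk 30%; risk r=5% in non-admitted patients; admission 80% on placebo and 100% on ketamine.

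- Overall risk, equal in all arms: 0.80×0.30 + 0.20×0.05 = 25%.
- ICU-set risk: placebo 30%; ketamine 25%, since all are admitted.

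False benefit means rejection in favour of ketamine. For Fisher (assumed two-sided 0.05, 20 v 20), sum over all tables. For either dose, the placebo arm is shared: sum over a of P(a)·[1-(1-q(a))²], where q(a) is the chance that one dose is significantly better given a placebo events.

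| Admission, placebo v ketamine | Fisher, per dose | Fisher, either dose | Pooled MH (sizing test only) |
|---|---|---|---|
| No difference | 1.2% | 2.3% | 5.0% |
| 90% v 100% | 1.9% | 3.5% | 7.4% |
| 80% v 100% | 2.8% | 5.1% | 10.7% |
| 100% v 80% | 0.4% | 0.8% | 1.7% |

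With r from 10% down to 0%, the 80% v 100% row runs 2.4-3.3%, 4.4-5.9% and 9.3-12.4%. In the last row, ketamine's ICU-set risk is (0.30 - 0.20×0.05)/0.80 = 36.3%, and if ketamine truly cut risk to one sixth (30% to 5%), pooled power would fall to 80%.

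**4. Illustration: early ICU discharge.** Assume 12 readings over POD 0-3, one ICU day (3 readings) lost, and constant hazard: 1-(1-0.30)^(9/12) = 23.5%. If 20% of ketamine patients only lose the day, their arm reads 0.2×23.5% + 0.8×30% = 28.7%, and false benefit for either dose is 2.9%, against 2.3% with no difference.

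**The case against.** The case for leaving the plan alone is substantial. No passage removes replaced patients; they stay in follow-up, and incidence by randomised group in section 10b fits an as-randomised analysis. Staff and provider are blinded. Section 4 hypothesises that ketamine will not increase ICU stay. The ICU outcomes that section 6 hopes to improve are delirium, cognition and pain control, not admission. Sections 2 and 6 describe per-shift screening without limiting it to the ICU, and section 8 also says available POD 1-3 data will come from the medical record. Section 2 calls it unusual for such a case to lack CAM-ICU data, so non-admission may be rare. The section 7 count of 60 is a recruitment target, and the Primary Aim also mentions cognitive dysfunction, which is measured at the late visit.

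Most of this stands as a limit on the claim. A reader might infer that replaced patients are excluded, or that the result will favour ketamine; the documents support neither. What remains is that blinding does not turn ICU admission into a baseline variable. Section 2 itself says ICU nursing performs the screens, and footnote 4 limits POD 0-3 readings to the ICU stay. Nothing in section 10 settles whether replaced patients count. Whatever the Primary Aim says about cognition, delirium status is settled on POD 3, so a missed clinic visit should not decide who counts for it.

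**Conclusion.** The point holds as a gap that should be closed before unblinding. The replacement rule, the CAM-ICU source and the missing analysis set together permit, but do not require, a primary comparison in a group formed after treatment. Any bias depends on ICU admission or ICU time differing by arm; its size and direction are unknown.

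Under assumed inputs and a 20-point admission gap, false benefit with the planned Fisher test reaches about 2.8% per dose and 5.1% for either dose. A reader might take the 10.7% figure as a doubled error rate for the trial. It belongs to the pooled one-sided test, which section 10a uses only for sizing, and it needs an admission gap that no document reports. Nor does the point count against the power statement: 85% reproduces.

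**What to change.** 1. **Section 7.** Replace the post-surgery trigger with planned postoperative ICU admission, confirmed before randomisation. Any later replacement may add patients but never removes anyone from the analysis.
2. **Section 10b, analysis set.** State that the primary set is all randomised patients who received study drug, analysed as randomised, whatever their ICU admission or attendance at the 2-6 week visit. Analyse ICU-admitted patients as a sensitivity analysis.
3. **Section 10b, readings.** Use every CAM-ICU reading charted on POD 0-3, in or out of the ICU; any positive is an event. Keep recovery-room readings out of the primary outcome, since section 6 does not name them, and add them in a sensitivity analysis. A patient with at least one post-operative reading that counts and no positive is a non-event in the primary analysis. Show best- and worst-case bounds for incomplete readings as a sensitivity analysis. A patient with no counted reading stays in the set as missing, is reported by arm and is covered by the same bounds.
4. **Completion.** Define it for the primary outcome as delirium status through POD 3. Reconcile sections 2, 6 and 8 and Appendix A on where and when CAM-ICU is recorded.
5. **Reporting.** Give ICU admission, ICU days and number of CAM-ICU readings by arm.

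**Cost.** One eligibility line, one changed rule and section 10 wording. Item 1 can help only patients not yet randomised; the rest can be fixed at any time before unblinding. Eligibility narrows slightly, unplanned non-admission can still occur, and some outcomes stay incomplete. Counting an early leaver without a positive as a non-event can miss late delirium, hence the bounds.

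If lower-risk non-ICU patients count within the 60, pooled-test power falls from 84.8% to 81-83% when they make up 10% of patients. It falls to 73-78% at 29%, the share if all (85-60)/85 of the planned non-completers were non-ICU patients. Both ranges assume a non-ICU placebo risk of 0-10% and the same sixfold ratio. Item 1 should keep that share low.

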Recently a small randomized trial in cardiac surgery patients found a significant reduction in postoperative delirium (31% to 3%) when sub-anaesthetic doses of ketamine (0.5mg/kg) were given upon induction [13]. The same group further published data for improved postoperative cognitive function with ketamine in cardiac patients [13]. A follow up randomized prospective study in cardiothoracic patients looking at ketamine and delirium is currently recruiting (PODCAST).

Ketamine's benefits are thought to be based on its NMDA antagonism, HCN1 inhibitory effects and its anti-inflammatory properties [14]. Multiple studies have shown decreased post-operative pain with decreased post-operative opioid use when ketamine was administered during the surgery [15]. Interestingly a recent study showed that a single dose of ketamine had a prolonged two week lasting effect on patients with refractory depression [16].

Ketamine is a drug that has been in use for more than half a century, is inexpensive and has a wide margin of safety.

We are proposing a prospective randomized placebo controlled study to elucidate the effects of ketamine on postoperative delirium in the head and neck cancer population receiving “flaps”, administered peri-operatively.

4. Objectives:

Primary Aim:

Optimize our intraoperative treatment protocol for head and neck cancer patients to reduce the incidence of delirium and associated postoperative cognitive dysfunction. The hypothesis is that ketamine decreases delirium postoperatively in this high risk surgical patient population.

Secondary Aims:

1. Determine the dose response relationship for intraoperative ketamine and delirium reduction. Our hypothesis is that higher dose ketamine will lead to a more profound reduction in postoperative delirium.
2. Determine if a single dose of ketamine will reduce post-operative pain and opioid requirements. Our hypothesis is that the higher dose of ketamine will lead to a more profound decrease in objective pain scores.
3. Determine if raw EEG data can predict postoperative delirium during general anesthesia. Our hypothesis is that EEG patterns will correlate with incidence of post-operative delirium.
4. Evaluate length of ICU and length of hospital stay (done by medical chart review). Our hypothesis is that ketamine administration will not increase ICU/hospital stay.

5. Innovation, Impact & Leverage.

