The Emory School of Medicine, section of Anesthesiology Research, will conduct this study according to the national rules, regulations and guidelines governing human clinical research. In addition, procedures cited by the US Code of Federal Regulations (Title 21) will be followed as these apply to the principles of Good Clinical Practices and approval by the Emory Institutional Review Board (IRB). Investigators will complete Emory University required research training. All individuals involved in the study and data collection will be made aware of the unanticipated event reporting policy.

The research team will monitor subjects randomized and treated in the study for adverse events related to the research through the final study visit in the ENT clinic. If the change from baseline is considered by the investigator to be part of the normal fluctuations of an underlying disease process, this shall not be reported as an adverse event (AE). If the change in baseline is considered by the investigator to be an untoward medical occurrence different from the standard of care, this medical occurrence shall be reported as an AE. Any event meeting serious adverse event criteria will be reported by the research team immediately to the PI via email or telephone and will be reported to the Institutional Review Board (IRB) per policy. The PI will also inform all investigators of the event via email. The common grading system will be used for adverse event reporting where Grade 1 is mild, Grade 2 moderate, Grade 3 severe, Grade 4 life-threatening or disabling, and Grade 5 death related to AE. Should emergency unblinding be required for the safety of the patient, the PI will contact the Investigational Drug Service responsible for the preparation and dispensing of the study medication.

October 8, 2019

All enrolled subjects will be followed and monitored per Emory standard of care for postoperative surgery. Subject data will be evaluated on an ongoing basis during the study visits to ensure continued subject safety. There will be no pre-specified formal stopping rule for safety. An interim safety analysis will be performed after 10 participants are enrolled in each arm to ensure ongoing subject safety.

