This monitoring plan is appropriate, since ketamine, an anesthetic drug, has an excellent safety profile and is commonly used in anesthetic practice. In addition, the doses used in this study are unlikely to cause major or minor side effects (e.g., emergence reactions, hallucinations).

10. Statistical analysis

a. Sample size:

It was assumed about 30% delirium incidence in our population by standard care [1] [2] [3].

Estimating 5-8 oropharyngeal cancer surgeries per week with a conservative enrollment rate of 50%, we will be able to recruit 130-208 patients in 12 months. We plan to enroll about 85 eligible patients in order to achieve 20 completed patients in each randomized group. For this pilot study, with this sample size we will have 85% statistical power under significant level of 0.05 to detect delirium incidence rate drop at least 30% (placebo) to 5% (two treatment arms combined) by one-sized Mantel Haenszel test, and such effect size is supported by an existing trial [13].

b. Data analysis:

For primary aim, the incidence of delirium will be calculated in each of three randomized group with 95% confidence interval (CI), and compared between each ketamine treated group with placebo group through Fisher's exact test. For secondary aims, the dose response effect of ketamine on delirium reduction will be tested by Cochran-Armitage trend test. For other outcomes, such as pain (and/or change from baseline), MMSE (and/or change from baseline), EEG data, length of stay (LOS), and use of narcotics will be first described by summary statistics (mean, median, standard deviation, frequency, and etc.) by three randomized groups and then compared by Chi-square test/Fisher's exact test, ANOVA, or Krusal-Wallis test wherever appropriate. The analysis will be

conducted by the Biostatistics and Bioinformatics Shared Resource at Winship Cancer Institute.

The Winship OnCore system will be used for data entry and analysis.

11. Confidentiality

The privacy of the research subjects will be ensured through standard procedures for securing research data. Whenever possible, a study number, rather than a name, will be used on study records. Identifying information will not appear when we present or publish the study results. All interactions with subjects during the study will occur in a private setting. Only Emory owned computers will be utilized to store data with any identifiers and these are compliant with the Emory disc encryption policy.

12. Literature:

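### The stated 85% power belongs to a pooled one-sided Mantel-Haenszel test that is never planned; each planned Fisher comparison has about 45% (two-sided) or 54% (one-sided) power if each dose arm has 5% delirium

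*Combined protocol and SAP*

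**What the plan says.** Section 10a (Sample size) sets the placebo rate: "It was assumed about 30% delirium incidence in our population by standard care". It sets the size: "We plan to enroll about 85 eligible patients in order to achieve 20 completed patients in each randomized group". Its claim is that "we will have 85% statistical power under significant level of 0.05"; the effect and the test behind this claim are given as "to detect delirium incidence rate drop at least 30% (placebo) to 5% (two treatment arms combined) by one-sized Mantel Haenszel test". The word before the test name is read here as one-sided, and the calculation below supports that reading.

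Section 10b (Data analysis) says that, for the primary aim, delirium incidence will be given for each of the three groups with a 95% confidence interval and "compared between each ketamine treated group with placebo group through Fisher's exact test". It states neither the sidedness of these tests nor any multiplicity adjustment. The only other delirium test in 10b is a Cochran-Armitage trend test, assigned to a secondary aim.

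The primary aim in section 4 is worded for ketamine as a whole: "The hypothesis is that ketamine decreases delirium postoperatively in this high risk surgical patient population". The first secondary aim adds that the higher dose should reduce delirium more.

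**The concern.** A power statement is useful only if it describes the test that will decide the primary question. Here 10a and 10b differ in three ways: the groups compared (pooled ketamine against placebo, or each dose against placebo), the test (Mantel-Haenszel or Fisher's exact) and the sidedness (one-sided, or not stated). The plan also gives the 5% rate only for the two arms combined, so it states no assumed rate for either comparison that it will actually run.

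Two things are at stake. First, a non-significant dose comparison could be read as evidence against ketamine on the strength of an 85% claim that does not apply to it. Second, with two candidate primary comparisons and no stated sidedness, the choice that decides significance could be made after the data are seen.

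**Working it through.** **Inputs.** From 10a: placebo 30%, ketamine 5% (arms combined), alpha 0.05, 20 completed patients per group. From 10b: Fisher's exact test, each dose against placebo. Assumption not in the plan: 5% in each dose arm. Other splits are tried in step 3. Power is the total binomial probability of all tables that reach significance.

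**1. Reproduce the 85%.** Let *a* be placebo events out of 20 and *m* total events out of 60. The uncorrected Mantel-Haenszel statistic for one stratum is

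z = (a − 20m/60) / √[20·40·m(60 − m) / (60²·59)],

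significant one-sided if z ≥ 1.645. Summed over all tables at 30% and 5%, power is **84.8%**. The two-sided version gives 74.0%, so the plan's figure is the one-sided one. The arithmetic in 10a is sound for the test it names.

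**2. Power of the planned test.** For Fisher's exact test at 20 versus 20, the smallest number of placebo events that reaches p ≤ 0.05 is:

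| Events in dose arm | 0 | 1 | 2 | 3 | 4 |
|---|---|---|---|---|---|
| Probability at 5% | 0.3585 | 0.3774 | 0.1887 | 0.0596 | 0.0133 |
| Placebo events needed, one-sided | 5 | 6 | 8 | 9 | 10 |
| Probability of that many or more at 30% | 0.7625 | 0.5836 | 0.2277 | 0.1133 | 0.0480 |
| Placebo events needed, two-sided | 5 | 7 | 9 | 10 | 11 |
| Probability of that many or more at 30% | 0.7625 | 0.3920 | 0.1133 | 0.0480 | 0.0171 |

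Multiply down the columns and add:

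- One-sided: 0.2733 + 0.2203 + 0.0430 + 0.0068 + 0.0006 = **54.4%**.
- Two-sided: 0.2733 + 0.1479 + 0.0214 + 0.0029 + 0.0002 = **44.6%** (0.4457 in full enumeration).

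Both comparisons share the placebo arm. Conditioning on its event count gives:

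| | Two-sided | One-sided |
|---|---|---|
| Each dose | 44.6% | 54.4% |
| At least one dose significant | 59.0% | 66.3% |
| Both doses significant | 30.1% | 42.5% |

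A simulation of 400,000 trials agreed with these figures to within 0.1 to 0.2 percentage points.

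**3. Other rates.**

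- Doses at 7% and 3% (average 5%): 35.2% and 55.9% two-sided, 45.7% and 63.6% one-sided. At least one: 61.9% or 68.2%.
- Doses at 10% and 0%, the most lopsided split that averages 5%: at least one dose is significant with probability about 76%, whichever the sidedness.
- The 31% and 3% that section 3 reports from the cardiac surgery trial: 58.9% two-sided, 66.7% one-sided per comparison.

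**4. Size needed.** At 30% versus 5%, Fisher's test first reaches 85% at 44 per arm two-sided (85.4%) or 37 one-sided (85.6%).

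**5. Why sidedness matters.** The plan's rates correspond to 6/20 on placebo and 1/20 in a dose arm. The one-sided Fisher p is

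[C(20,6)·C(20,1) + C(20,7)·C(20,0)] / C(40,7) = (775,200 + 77,520) / 18,643,560 = 0.046.

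With equal arms the two-sided p is double that, 0.091. The pooled table, 6/20 against 2/40, gives Fisher p = 0.013 either way.

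**The case against.** - **It is a pilot.** The title and the power sentence both say so, and 10b plans confidence intervals for each arm. This lowers the stakes, and low power is acceptable in a pilot. It does not make a formal 85% claim true of a test that has roughly half that chance.
- **The 5% per arm is the reviewer's assumption.** Correct, and it sits awkwardly with the plan's own expectation of a stronger effect at the higher dose. Per-comparison power moves a good deal with the split: at 10% and 0% it is 24.2% and about 76% two-sided. No split examined reaches 85%.
- **One-sided is the natural reading.** Section 10a is one-sided and the primary hypothesis is directional, so 54% may be nearer the intention than 45%. Since that hypothesis concerns ketamine rather than each dose, the chance of at least one significant dose (66.3% one-sided) may be the fairer counterpart to the 85%. Both are reasonable readings, and both still fall short.
- **The trend test uses all 60 patients.** Its one-sided power is 77.9% at 5% and 5%, and 84.8% at 7% and 3% (68.4% and 76.4% two-sided). So not every planned delirium test is near 50%. But the trend test is secondary, and its power cannot stand in for that of the primary analysis.
- **The 6/20 against 1/20 table is a single outcome.** It shows only that sidedness must be stated; the power figures carry the main point.

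**Conclusion.** The concern holds. The 85% is calculated correctly but for an analysis the plan does not contain. With 20 per arm and 30% against 5%, each planned comparison has 44.6% power two-sided or 54.4% one-sided, a shortfall of about 30 to 40 percentage points. Counting success as at least one significant dose gives 59.0% or 66.3%, and at most about 76% under any split that averages 5%. The figures assume 20 completed patients per arm, the plan's 30% placebo rate and no multiplicity adjustment. The per-comparison headline also assumes 5% in each dose arm. No bias or inflated false-positive rate follows from the planned tests; the fault is a power claim that does not match the primary analysis, together with unstated sidedness.

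**What to change.** State the sidedness in 10b, then choose one of two routes.

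**(a) Default: keep the Fisher comparisons as primary.** Replace the power sentence in 10a with, for example: *With 20 completed patients per group, each dose compared with placebo by Fisher's exact test at 0.05 has about 45% (two-sided) [or 54% (one-sided)] power for 30% versus 5%.* No multiplicity reduction is needed: at this size Fisher's test is conservative, and the two unadjusted tests together have a familywise error of at most 4.7% two-sided or 4.9% one-sided. The cost is one sentence and the sidedness. There are no extra patients and no design change, but the stated power is less favourable.

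**(b) Alternative: make pooled ketamine against placebo the primary test.** This fits the primary hypothesis, with the dose comparisons and trend test secondary. It is open only if decided before anyone choosing the analysis has seen delirium by arm, which matters because section 9c says "An interim safety analysis will be performed after 10 participants are enrolled in each arm". A size-controlled test such as Boschloo's would have about 79% power one-sided or 73% two-sided. If the uncorrected Mantel-Haenszel test is kept, 10a should say that its true one-sided size, although 5.0% at a common rate of 30%, rises to about 6.4% at common rates near 7.5%. The cost is a dated amendment and confirmation that those deciding have not seen delirium by arm. No extra patients are needed, but the main claim becomes one about ketamine overall, not each dose.
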